5.0 DOSE MODIFICATIONS FOR TOXICITIES

5.1 Carboplatin

5.1.1 Nephrotoxicity

Patients who have compromised renal function should undergo a GFR (see table in [Section 3.2.6.2](#)). If the corrected GFR is $<100 \text{ mL/min/1.73m}^2$, the carboplatin dose should be calculated per the modified Calvert Formula using a target AUC of 5. **Please note that the equation below calculates the ACTUAL mg of carboplatin to be given and NOT the dose per surface area. Also note that the maximum dose calculated using the modified Calvert Formula must not exceed the originally planned dose of 600 mg/m^2 . Each final total daily dose of carboplatin should be checked to ensure that it does not exceed this amount.**

Modified Calvert Formula:

$$\text{Carboplatin Total Dose in mg/day} = \frac{\{(\text{Corrected GFR} \times \text{surface area}) + (15 \times \text{surface area})\} \times \text{AUC}}{1.73}$$

Alternately, the equation may also be expressed as follows:

$$\text{Carboplatin Total Dose in mg/day} = \frac{\{(\text{Uncorrected GFR}) + (15 \times \text{surface area})\} \times \text{AUC}}{1.73}$$

Example Carboplatin dosage calculation:

Example 1:

$$\text{Surface area} = 0.5\text{m}^2$$

$$\text{Corrected GFR} = 70\text{mL/min/1.73m}^2$$

$$\text{Total dose in mg/day} = \frac{\{70 \times 0.5 + 15(0.5)\} \times 5}{1.73}$$

$$\text{Dose} = (20.23 + 7.5) \times 5 = 139 \text{ mg/day}$$

Double check dose to ensure that it does not exceed 600 mg/m^2 :

$$139 \text{ mg} \div 0.5 \text{ m}^2 = 278 \text{ mg/m}^2$$

This does not exceed the max dose of 600 mg/m^2 , so 139 mg is acceptable.

Example 2:

$$\text{Surface area} = 1.2\text{m}^2$$

$$\text{UN-corrected GFR} = 50\text{mL/min}$$

$$\text{Total dose in mg/day} = \{50 + 15(1.2)\} \times 5$$

$$\text{Dose} = (50 + 18) \times 5 = 340 \text{ mg/day}$$

Double check dose to ensure that it does not exceed 600 mg/m^2 :

$$340 \text{ mg} \div 1.2 \text{ m}^2 = 283 \text{ mg/m}^2$$

This does not exceed the max dose of 600 mg/m^2 , so 283 mg is acceptable.

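### Carboplatin Example 2 in Section 5.1.1 calculates 340 mg/day but closes by accepting 283 mg, the figure from its per-m² check

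*Combined protocol and SAP*

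**What the plan says.** Section 5.1.1 (Nephrotoxicity, under carboplatin) applies when the corrected GFR is below 100 mL/min/1.73 m². The dose is then to come from the "modified Calvert Formula using a target AUC of 5". A note in bold explains what the formula returns: "the equation below calculates the ACTUAL mg of carboplatin to be given and NOT the dose per surface area". The result "must not exceed the originally planned dose of 600 mg/m^2", and each example divides its calculated total by surface area to test this.

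Example 1 (0.5 m², corrected GFR 70) calculates 139 mg/day, obtains 278 mg/m² in the check, and ends "so 139 mg is acceptable".

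Example 2 (1.2 m², uncorrected GFR 50 mL/min) calculates 340 mg/day, obtains 283 mg/m² in the check, and ends "so 283 mg is acceptable".

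The carboplatin rows of the therapy delivery maps in Sections 4.3.2 and 4.4.2 refer sites to Section 5.1.1 when renal function is abnormal. Carboplatin is given in Cycles 1, 3 and 5 of Stratum 1 and in all four cycles of Stratum 2.

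**The concern.** The two examples follow the same steps but end differently. Example 1 ends on the calculated total in mg. Example 2 ends on the number from the ceiling check, with its unit changed from mg/m² to mg. Example 2 therefore offers two figures for one patient's total dose, 340 mg on the calculation line and 283 mg on the closing line, and they cannot both be right. This is the confusion that the bold note is there to prevent.

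A worked example is meant to be followed. A site that copies the closing step of Example 2 could record a per-m² number as the total for a child or young adult with reduced renal function. That is a safety matter. It would also add variation in delivered chemotherapy that the plan does not intend.

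**Working it through.** All inputs come from Section 5.1.1 unless stated otherwise.

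**Reproducing Example 2** (surface area 1.2 m², uncorrected GFR 50 mL/min, AUC 5)

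- Calculation, as worked in the example: (50 + 15 × 1.2) × 5 = (50 + 18) × 5 = 340 mg/day. This matches the stated figure.
- Check: 340 / 1.2 = 283.3 mg/m². This matches the stated 283 mg/m².
- Closing line: 283, now in mg.

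The first two lines each reproduce. The conflict arises only at the closing line.

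**Reproducing Example 1** (surface area 0.5 m², corrected GFR 70, AUC 5)

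- Calculation: (70 × 0.5 / 1.73 + 15 × 0.5) × 5 = (20.23 + 7.5) × 5 = 138.7, stated as 139 mg/day.
- Check: 139 / 0.5 = 278 mg/m².
- Closing line: 139 mg. The example is internally consistent.

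**Can 283 mg be a total dose by some other route?**

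- Through the ceiling: 600 × 1.2 = 720 mg. The calculated 340 mg is well below it, so the ceiling calls for no reduction.
- Dividing the whole bracket by 1.73: 340 / 1.73 = 196.5 mg.
- Dividing only the GFR term by 1.73: (50 / 1.73 + 18) × 5 = 234.5 mg.
- Converting to corrected GFR first: 50 × 1.73 / 1.2 = 72.1 mL/min/1.73 m², and the first formula then gives (72.1 × 1.2 / 1.73 + 18) × 5 = 340 mg.

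None of these gives 283 mg.

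**Size of the discrepancy in Example 2 if 283 is read as total mg**

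- Relative to the calculation line: 1 − 283/340 = 16.8% lower.
- Per surface area: 283 / 1.2 = 235.8 mg/m², not the 283 mg/m² that was checked.
- Implied AUC: 283 / (50 + 18) = 4.16, against the stated target of 5.

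**Dependence on body size**

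Putting the check value in place of the total multiplies the figure by 1/BSA. The two agree only at 1.0 m². Above that the substituted figure is lower than the calculated one, and below it is higher. For Example 1's patient the substitution gives 278 mg against a calculated 139 mg, a factor of 2, with an implied AUC of 278 / 27.73 = 10.0. The section's own ceiling check would not flag this, because 278 / 0.5 = 556 mg/m² is still under 600 mg/m².

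**Could such a patient be on study?**

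Section 3.2.6.2 admits a GFR of 70 mL/min/1.73 m² or more, and the formula applies below 100. Example 2's corrected GFR of 72.1 lies between the two.

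**The case against.** The strongest reply is that the sentence closes an illustration and is not the rule. The formula, the AUC target and the ceiling are untouched by it. The 340 mg/day line stands just above it, Example 1 shows the step consistently, and the bold note says what the formula returns. The therapy delivery maps also require each patient's own surface area and calculated dose to be entered. A careful pharmacist may well notice the conflict. The documents do not say how many patients would be dosed by this formula, and nothing in them shows that anyone was misdosed.

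All of that stands, and it limits the claim to what could happen if a site follows the example's last step. It does not remove the contradiction. The closing line is ordinary running text, so an error in reading the PDF is unlikely, and no other section corrects it. The delivery maps lead sites to this page.

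One related observation carries little weight. The alternate formula for uncorrected GFR appears with a divisor of 1.73 that Example 2 does not use. This may be a layout artefact. The first formula also appears with the divisor under the whole bracket, which for Example 1 would give (35 + 7.5) × 5 / 1.73 = 122.8 mg, whereas the worked line divides only the GFR term and obtains 139 mg. The fraction layout in the text as read therefore cannot be relied on. The main point does not depend on it.

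**Conclusion.** The concern holds. Example 2's closing line contradicts its own calculation line, the pattern of Example 1 and the section's statement of what the formula returns. The two figures for the same patient, 340 mg and 283 mg, differ by 16.8%. Neither the dose ceiling nor any variant of the formula that was tried accounts for the difference. If the closing step were copied for other patients, the discrepancy would scale as 1/BSA and could run in either direction.

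The arithmetic rests only on figures printed in the section. The consequence for patients is conditional on a site following the closing line, and its frequency cannot be estimated from the documents. The sample sizes, endpoints and analyses do not depend on this text. Correction is nonetheless required, because the passage is used for dosing patients with reduced renal function. Which figure should stand is for the sponsor to decide.

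**What to change.** Reconcile the calculation, check and closing lines of Example 2 with one another, with Example 1 and with the bold note on what the formula returns. While the section is open, compare both printed formulas in the source file with the arithmetic in both examples, to settle whether the 1.73 divisor in the alternate formula is a layout effect. The sponsor determines the correct dose text.

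The cost is a one-line correction in an amendment and a notice to sites. No change to the design or the analysis follows from it.

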5.1.2 Ototoxicity

Careful monitoring of children by expert audiologist and by serial audiometry throughout the treatment with carboplatin is recommended as clinically indicated. Otoacoustic emissions (OAE) are the clinical methodology of choice for initial testing. If these are normal, patients do not need further evaluation, and should be coded as having no hearing loss. If they are abnormal, then brainstem evoked auditory responses (BAER) or tone audiometry should be used to more specifically describe the hearing loss. A decrease in auditory acuity at frequencies above 4000 Hz is expected and does not constitute a contraindication to further therapy. For Grades 0, 1 and 2 ototoxicity (CTCAE) no dose modification is recommended. For Grade 3 toxicity, a 50% reduction should be made in the carboplatin dosage. For Grade 4 ototoxicity, carboplatin can be continued at 50% dose reduction or discontinued at the discretion of treating physician and family.

5.1.3 Allergic Reactions

Carboplatin allergic reactions may be managed with pre-medications such as diphenhydramine 1 mg/kg IV (maximum dose 50 mg), ranitidine 1 mg/kg IV (maximum dose 50 mg) and hydrocortisone 4 mg/kg IV (maximum dose 100 mg).

5.1.4 Hematologic Toxicity

If counts are slow to recover after Cycle A, use filgrastim (G-CSF) during subsequent Cycle A.

5.2 Etoposide

5.2.1 Nephrotoxicity

In patients with impaired renal function, the following initial dose modification should be considered based on measured creatinine clearance:

Measured CrCL	> 50 mL/min/1.73m ²	15-50 mL/min/1.73m ²
Etoposide Dose	100% of Dose	75% of Dose

Subsequent dosing should be based on patient tolerance and clinical effect. Data are not available in patients with creatinine clearances of < 15 mL/min and further dose reduction should be considered in these patients.

5.2.2 Hepatotoxicity

If the direct bilirubin is between 2 and 3 mg/dL, give 50% of the calculated dose of etoposide. If the direct bilirubin is > 3 mg/dL, hold the etoposide. Full dose may resume when the direct bilirubin has fallen to < 1.2 mg/dL.

5.2.3 Allergic Reactions

Etoposide allergic reactions may be managed with pre-medications such as diphenhydramine 1 mg/kg IV (maximum dose 50 mg), ranitidine 1 mg/kg IV

(maximum dose 50 mg), and hydrocortisone 1-2 mg/kg IV (maximum dose 100 mg), and by slowing the rate of the infusion. For those reactions, which are unable to be controlled with pre-medication and slowing of the rate of etoposide infusion, etoposide phosphate may be substituted in the same dose and at the same rate. Pre-medication for etoposide phosphate is recommended.

5.3 Ifosfamide

5.3.1 Hematologic

No modifications of subsequent chemotherapy cycles will be made for delayed recovery of neutrophil or platelet counts, following a prior cycle of Induction chemotherapy.

5.3.2 Hemorrhagic Cystitis

Microscopic Hematuria

For transient microscopic hematuria (no more than 2 abnormal urinalyses on 2 separate days during a cycle of therapy), there is no modification of the ifosfamide or mesna dose.

For persistent microscopic hematuria (> 2 abnormal urinalyses during a cycle of therapy), increase hydration to 3500-4000 mL/m²/day. In addition, if mesna administration is oral or by intermittent intravenous bolus, convert to continuous intravenous mesna.

Gross Hematuria

All episodes of gross hematuria should be evaluated in conjunction with a pediatric surgery/urology consult. Further testing, such as cystoscopy, urine culture, excretory urogram, and voiding cystogram should be considered based on good clinical judgment.

For transient gross hematuria (only 1 episode, which clears to less than gross hematuria) during or following a cycle of therapy, hold ifosfamide until hematuria clears. When hematuria clears, restart at 50% of the previous ifosfamide dose. Use hydration of 3500-4000 mL/m²/day and mesna at 100% of ifosfamide dose as a continuous infusion over 24 hrs/day. The ifosfamide dose may be escalated back to 100% if tolerated.

For persistent gross hematuria after completion of a cycle of therapy, hold subsequent ifosfamide until the urine clears to less than gross hematuria. Reinstigate ifosfamide at 50% of the initial dose, with hydration of 3500-4000 mL/m²/day and the mesna at 100% of the ifosfamide dose administered as a continuous infusion over 24 hours. If this regimen is tolerated, the ifosfamide dose may be escalated back to the original dose (100%).

For persistent gross hematuria occurring during a cycle of ifosfamide, interrupt the ifosfamide. Withhold further ifosfamide until the next cycle of therapy or until urine clears. Reinstigate ifosfamide at 50% of the initial dose, with hydration of 3500-4000 mL/m²/day and the mesna at 100% of the ifosfamide dose administered as a continuous infusion over 24 hours. If this regimen is tolerated, the ifosfamide dose may be escalated back to the original dose (100%).

For persistent gross hematuria on the mesna continuous infusion regimen, discontinue the ifosfamide.

5.3.3 Nephrotoxicity

In patients with a measured creatinine clearance <10 mL/min/1.73m², decrease dose by 25% (give 75% of initial dose).

5.3.4 Neurotoxicity

This is an organic brain syndrome that ranges from mild confusion and disorientation to seizures, ataxia, and coma. It may be aggravated by impaired renal function. It usually, but does not always, resolve spontaneously, and it may or may not recur with subsequent doses. If symptoms are mild and transient cycle may continue with strict avoidance of potentially aggravating co-administered medications such as sedatives and anticholinergic drugs. If Grade 4 neurotoxicity occurs during ifosfamide administration, investigators may consider administration of methylene blue. Patients who have experienced mild symptoms (\leq Grade 2) may receive ifosfamide in subsequent cycles. If neurotoxicity $>$ Grade 2 occurs or symptoms are prolonged, delete ifosfamide from all subsequent cycles .

6.0 DRUG INFORMATION

See the consent document for toxicities. All other information is available on the COG website in the commercial agent monographs manual titled “Drug Information for Commercial Agents used by the Children’s Oncology Group.” This manual is provided under Standard Sections for Protocols at: https://members.childrononcologygroup.org/prot/reference_materials.asp.

7.0 EVALUATIONS/MATERIAL AND DATA TO BE ACCESSIONED

Timing of protocol therapy administration, response assessment studies, and surgical interventions are based on schedules derived from the experimental design or on established standards of care. Minor unavoidable departures (up to 72 hours) from protocol directed therapy and/or disease evaluations (and up to 1 week for surgery) for valid clinical, patient and family logistical, or facility, procedure and/or anesthesia scheduling issues are acceptable per COG administrative Policy 5.14 (except where explicitly prohibited within the protocol).

7.1 Required Clinical, Laboratory and Disease Evaluations During Protocol Therapy

All baseline studies must be performed prior to starting protocol therapy unless otherwise indicated below. **Obtain other studies prior to start of phase unless otherwise indicated.**

STUDIES TO BE OBTAINED	Baseline	Prior to Each Cycle of Induction (Cycles A and B)	During Induction (Cycles A and B)	Completion of Induction (Day 21-35)	Following Second-Look Surgery	Within 2 Weeks Prior to Starting RT	During Radiation Therapy	Between 4 -6 Weeks following Completion of Therapy
History	X	X		X	X		X (Weekly If Clinically Indicated)	
Physical Exam (Ht, Wt, VS) with Neurologic Exam	X	X		X	X			X
Performance Status	X	X		X	X			X
CBC (differential, platelets)	X	X	X (Weekly)	X	X	X	X (Weekly If Clinically Indicated)	X
Urinalysis	X	X		X				X
Electrolytes (including BUN, Calcium, PO ₄ , Magnesium, Sodium, Potassium)	X	X	X (Weekly if Clinically Indicated)	X	X			X
Serum Creatinine, Creatinine Clearance or GFR	X			X				
Total protein, AST, ALT, albumin, bilirubin	X	X						X
Lumbar CSF Cytology ⁴	X			X				X
CSF Markers (hCG, AFP) ⁶	X			X				X
Serum markers (hCG, AFP)	X		X (After Cycles 2 and 4)	X	X	X		X
Brain MRI with and without gadolinium ¹	X		X (After Cycles 2 and 4)	X	X			X
Spine MRI	X ²			X ⁵				X ⁵
Audiogram or BAER	X			X				X
Endocrine Function ³	X			X				X
Pregnancy test (for females of childbearing potential)	X							

1- All patients must have a cranial MRI with and without gadolinium at diagnosis/prior to enrollment. If surgical resection is performed, patients must have pre-operative and post-operative cranial MRI with and without gadolinium. The post-operative brain

MRI should be obtained within 72 hours of surgery. If patient has a biopsy only, post-operative cranial MRI is recommended but not required.

2 - All patients must have a spine MRI with gadolinium obtained at diagnosis/prior to enrollment. Note: If the spine study is performed for the first time after surgical resection or biopsy, it is recommended to be obtained with and without gadolinium.

3 - Endocrine evaluation to include: Cortisol (8 AM), TSH, free T4, IGF1 and IGF BP3. Tanner Stage, LH, FSH, estradiol, and testosterone if child has precocious puberty before age 8 in girls or 9 in boys or for all patients age 11 or greater.

4 - Lumbar CSF cytology should be obtained unless medically contraindicated.

5 - Spinal MRI with gadolinium is sufficient.

6 - Lumbar CSF markers must be obtained unless medically contraindicated. If possible determine CSF markers and serum markers on the same day. If lumbar CSF markers are contraindicated, ventricular CSF markers are acceptable. In case CSF diversion and biopsy/surgery is combined, ventricular CSF should be collected first.

This table only includes evaluations necessary to answer the primary and secondary aims. Obtain other studies as indicated for good clinical care.

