3.2 Patient Eligibility Criteria

Important note: The eligibility criteria listed below are interpreted literally and cannot be waived (per COG policy posted 5/11/01). All clinical and laboratory data required for determining eligibility of a patient enrolled on this trial must be available in the patient's medical/research record which will serve as the source document for verification at the time of audit.

All clinical and laboratory studies to determine eligibility must be performed within 14 days prior to enrollment. Laboratory values need not be repeated if therapy starts within 14 days of obtaining labs to assess eligibility. If a post-enrollment lab value is outside the limits of eligibility, or laboratory values are >14 days old, then the following laboratory evaluations must be re-checked within 48 hours prior to initiating therapy: CBC with differential, bilirubin, ALT (SGPT) and serum creatinine. If the recheck is outside the limits of eligibility, the patient may not receive protocol therapy and will be considered off protocol therapy. Imaging studies must be obtained as outlined in [Section 3.2.3](#).

See [Section 7.1](#) for required studies to be obtained prior to starting protocol therapy.

INCLUSION CRITERIA

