3.2.6 Organ Function Requirements

3.2.6.1 Adequate Bone Marrow Function Defined As:

- Peripheral absolute neutrophil count (ANC) $\geq 1,000/\mu\text{L}$
- Platelet count $\geq 100,000/\mu\text{L}$ (transfusion independent)
- Hemoglobin ≥ 8.0 g/dL (may receive RBC transfusions)

3.2.6.2 Adequate Renal Function Defined As:

- Creatinine clearance or radioisotope GFR ≥ 70 mL/min/1.73 m² or
- A serum creatinine based on age/gender as follows:

Age	Maximum Serum Creatinine (mg/dL)	
	Male	Female
2 to < 6 years	0.8	0.8
6 to < 10 years	1	1
10 to < 13 years	1.2	1.2
13 to < 16 years	1.5	1.4
≥ 16 years	1.7	1.4

The threshold creatinine values in this Table were derived from the Schwartz formula for estimating GFR (Schwartz et al. J. Peds, 106:522, 1985) utilizing child length and stature data published by the CDC.

3.2.6.3 Adequate Liver Function Defined As:

- Total bilirubin ≤ 1.5 x upper limit of normal (ULN) for age, and
- SGOT (AST) and SGPT (ALT) < 2.5 x upper limit of normal (ULN) for age.

3.2.6.4 Central Nervous System Function Defined As:

- Patients with seizure disorder may be enrolled if well controlled.
- Patients must not be in status, coma or assisted ventilation prior to study

enrollment.

EXCLUSION CRITERIA

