CARBOplatin (CARBO)	IV over 15-60 minutes	600 mg/m ² /dose	1	See Section 5.1.1 if renal function is abnormal.	a. History, PE (Ht, Wt, VS) with Neurologic Exam, Performance Status b. CBC (differential, platelets) c. Urinalysis
Etoposide (ETOP)	IV over 60-120 minutes	150 mg/m ² dose	1-3	See admin guidelines in Section 4.3.1	d. Electrolytes (including BUN, Calcium, PO ₄ , Magnesium, Sodium, Potassium) e. Total protein, AST, ALT, albumin, bilirubin OBTAIN OTHER STUDIES AS REQUIRED FOR GOOD PATIENT CARE

Enter Cycle #: _____ Ht _____ cm Wt _____ kg BSA _____ m²

Date Due	Date Given	Day	CARBO mg	ETOP mg	Studies	Comments (Include any held doses, or dose modifications)
			Enter calculated dose above and actual dose administered below			
		1	_____ mg	_____ mg	a, b, c, d, e	
		2		_____ mg		
		3		_____ mg		
		4				
		8			b, d [@]	
		15			b, d [@]	
		22	Start Cycle B on Day 22 or when blood count parameters are met (whichever occurs later).			

@ Obtain weekly if clinically indicated.

See [Section 5.0](#) for Dose Modifications for Toxicities and the COG website posted materials for Supportive Care Guidelines.

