
4.3.4 Stratum 1 NGGCT Cycle B Induction Induction consists of six cycles (Cycle A and Cycle B). Cycle B is given during Cycles 2, 4 and 6. This Cycle lasts 3 weeks (21 days).
	
_____
 
Patient name or initials
 
_____
 
DOB

---	--

Criteria to start this cycle: ANC > 1,000/ μ L and platelets > 100,000/ μ L and off filgrastim (G-CSF) for at least 48 hours. Extensive details are in [Section 4.0](#) (treatment overview). This cycle lasts 21 days and the TDM for this cycle is on 1 page.

DRUG	ROUTE	DOSAGE	DAYS	IMPORTANT NOTES	OBSERVATIONS
Ifosfamide (IFOS)	IV over 60 minutes	1800 mg/m ² /dose	1-5	See admin guidelines in Section 4.3.3	a. History, PE (Ht, Wt, VS) with Neurologic Exam, Performance Status b. CBC (differential, platelets) c. Urinalysis d. Electrolytes (including BUN, Calcium, PO ₄ , Magnesium, Sodium, Potassium) e. Serum Creatinine, CrCl or GFR f. Total protein, AST, ALT, albumin, bilirubin g. Lumbar CSF cytology* h. Lumbar CSF Markers (hCG, AFP)* i. Serum Markers (hCG, AFP) j. Brain MRI with and without gadolinium k. Spine MRI with and without gadolinium l. Audiogram or BAER m. Endocrine function * Lumbar CSF should be obtained unless medically contraindicated. OBTAIN OTHER STUDIES AS REQUIRED FOR GOOD PATIENT CARE
Etoposide (ETOP)	IV over 60-120 minutes	100 mg/m ² /dose	1-5	See admin guidelines in Section 4.3.3	
Mesna (MESNA)	IV (short or continuous infusion)	See Section 4.3.3	1-5	Administer concurrently with ifosfamide	
Filgrastim (G-CSF)	SubQ (preferred) or IV	5 mcg/kg/dose	Daily on Days 6-15	Start G-CSF on Day 6 and continue for ten days or until ANC > 1500/ μ L.	

Enter Cycle #: _____ Ht _____ cm Wt _____ kg BSA _____ m²

Date Due	Date Given	Day	IFOS _____mg	ETOP _____mg	MESNA _____mg	G-CSF _____mcg	Studies	Comments (Include any held doses, or dose modifications)	
			Enter calculated dose above and actual dose administered below						
		1	_____mg	_____mg	_____mg		a, b, c, d, e, f		
		2	_____mg	_____mg	_____mg				
		3	_____mg	_____mg	_____mg				
		4	_____mg	_____mg	_____mg				
		5	_____mg	_____mg	_____mg				
		6				_____mg			
		8					b, d@		
		15					b, d@		
		21					I\$, j\$ [a,b,c,d,e,f,g, h,i,j,k,l,m]#	Indicate date of last G-CSF dose _____	
		22	Start Cycle A on Day 22 or when blood count parameters are met (whichever occurs later). Upon completion of Induction, patients will undergo response evaluation.						

\$ Obtain after cycles 2 and 4

@ Obtain weekly if clinically indicated.

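### No creatinine or GFR is scheduled before carboplatin cycles after Cycle 1, although Section 5.1.1 makes the carboplatin dose depend on renal function; the gap is widest in Stratum 2 Cycles 2–4

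*Combined protocol and SAP*

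**What the plan says.** **Dose rule.** Both Cycle A maps (Sections 4.3.2 and 4.4.2) set carboplatin at 600 mg/m² and send the reader to Section 5.1.1 "if renal function is abnormal". Section 5.1.1 begins "Patients who have compromised renal function should undergo a GFR (see table in", the reference being to Section 3.2.6.2. That section accepts either a clearance or GFR of at least 70 mL/min/1.73 m², or "A serum creatinine based on age/gender as follows". If the corrected GFR is below 100, Section 5.1.1 replaces the default with a modified Calvert dose at AUC 5. The dose is capped at 600 mg/m², so the rule can only lower it.

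**Schedule.** In the Section 7.1 table, the row "Serum Creatinine, Creatinine Clearance or GFR" is marked at baseline and at completion of induction. The column for tests before each induction cycle is blank in that row.

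- Stratum 1 Cycle A map: Day 1 is a to e, and the legend ends at "e. Total protein, AST, ALT, albumin, bilirubin OBTAIN OTHER STUDIES AS REQUIRED FOR GOOD PATIENT CARE". It has no creatinine item.
- Stratum 2 Cycle A map: creatinine is item e, but Day 1 lists a, b, c, d and f. Item e appears only in the set due after Cycle 4.
- Stratum 1 Cycle B map: "e. Serum Creatinine, CrCl or GFR" is in the legend, and Day 1 lists a to f, so it is required before each ifosfamide course.

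The criteria for starting a cycle (Section 4.1 and the maps) concern blood counts and G-CSF only.

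**The concern.** A dose rule can be applied reliably only if its input is collected before the dose. Here the maps tell the treating physician to act on abnormal renal function, but the carboplatin-day schedule does not include the test that would show it. A site doing exactly what the table and maps list could give Stratum 2 Cycles 2, 3 and 4 at full dose with no creatinine, clearance or GFR since baseline. In Stratum 1, carboplatin Cycles 3 and 5 would rest on a value taken before the intervening ifosfamide.

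There is also an internal disagreement. The Section 7.1 column covers Cycles A and B together and is blank for creatinine, while the Cycle B map requires creatinine on Day 1.

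At stake is avoidable carboplatin overexposure in a child or young adult whose renal function has fallen during induction.

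**Working it through.** **1. Age of the last scheduled value.** Inputs: 21-day cycles (Section 4.1), Day 1 codes from the three maps, and the Section 3.2 rule that "Laboratory values need not be repeated if therapy starts within 14 days of obtaining labs to assess eligibility". Older values must be rechecked within 48 hours of starting. The baseline creatinine is therefore taken as 0–14 days old at Cycle 1, and Cycle 1 is covered.

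Stratum 2, with no scheduled value after baseline until the end of induction: age at Cycle k Day 1 = 21(k−1) to 21(k−1)+14 days.

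- Cycle 2: 21–35 days
- Cycle 3: 42–56 days
- Cycle 4: 63–77 days, after 3 × 600 = 1,800 mg/m² of carboplatin

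Stratum 1: creatinine is due on Day 1 of Cycles 2 and 4, so at Cycles 3 and 5 it is about 21 days old. It predates a planned 5 × 1,800 = 9,000 mg/m² of ifosfamide.

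These ages assume on-time cycles. Each cycle starts on Day 22 or at count recovery, whichever is later, so delays lengthen them.

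**2. Reproducing the plan's dose examples.** Dose in mg = (corrected GFR × BSA/1.73 + 15 × BSA) × AUC.

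- Section 5.1.1 Example 1 (BSA 0.5, corrected GFR 70, AUC 5): (20.23 + 7.5) × 5 = 138.7 mg. The plan states 139.
- Example 2 (BSA 1.2, uncorrected GFR 50): (50 + 18) × 5 = 340 mg. The plan states 340.

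The formula is read correctly.

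**3. What the rule would change.** Per m², dose = (GFR/1.73 + 15) × 5. Two illustrative values below the Section 3.2.6.2 floor of 70:

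- GFR 60: (34.68 + 15) × 5 = 248.4 mg/m². The default 600 is 600/248.4 = 2.42 times higher.
- GFR 50: (28.90 + 15) × 5 = 219.5 mg/m². The default is 600/219.5 = 2.73 times higher.

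Both assume that an abnormal creatinine prompts the GFR. Neither says how often such a fall occurs.

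**The case against.** The best defence is that the pattern looks consistent rather than accidental. The table and both Cycle A maps leave creatinine off, and it is required only before ifosfamide. Urinalysis and electrolytes with BUN are due before every cycle. The note under the Section 7.1 table says that it covers only what the study aims need and leaves other tests to good clinical care; the maps carry a similar line. The administration sections also refer to external group guidelines on monitoring, which are not part of these documents and may call for pre-dose renal tests.

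Part of this stands. Many sites will probably test anyway, and stricter testing before ifosfamide may well be deliberate. But these provisions permit a creatinine without scheduling one. The table's note does not explain the omission, because the same table requires urinalysis, electrolytes and liver tests before each cycle. BUN and urinalysis are not the trigger that Section 5.1.1 uses. And carboplatin has its own renal rule, whatever is done for ifosfamide.

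Two stronger readings are tempting and should not be adopted.

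- *That the etoposide rule is equally unsupported.* Section 5.2.1 begins "In patients with impaired renal function, the following initial dose modification should be considered based on measured creatinine clearance", but it describes an initial modification and then bases later dosing on tolerance and clinical effect. It does not clearly need a new value each cycle.
- *That the gap can be sized by the dose at GFR 70.* That is the eligibility floor, where renal function counts as adequate. Such a patient's creatinine may lie within the age and sex maxima, so a Day 1 creatinine need not lead to a GFR, and the dose might be 600 mg/m² with or without the added test.

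**Conclusion.** The point holds as a scheduling gap for the carboplatin rule. Section 5.1.1 needs evidence of compromised renal function, and none of the values it relies on is scheduled before Stratum 2 Cycles 2–4. Before Stratum 1 Cycles 3 and 5 only a pre-ifosfamide value is available. Cycle 1 is adequately covered.

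The schedule and the ages of the values follow directly from the maps and the table, assuming on-time cycles and a baseline 0–14 days old. The dose figures are illustrations of what is at stake for an individual patient below the eligibility floor, not an estimate of harm. The documents give no rate of renal decline during induction, so the number of patients affected is unknown. Nor would a Day 1 creatinine detect every GFR below 100, since some falls leave creatinine within the Section 3.2.6.2 maxima.

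A reader might also infer that the trial's conclusions are weakened. The documents do not support that: the 3-year PFS endpoint, the sample sizes of 77 and 79 and the error rates do not depend on this test. It is an inexpensive patient-safety improvement.

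**What to change.** Three edits:

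1. Add serum creatinine to the legend and Day 1 of the Stratum 1 Cycle A map (Section 4.3.2), with a GFR if it is abnormal, as Section 5.1.1 already provides.
2. Add item e to Day 1 of the Stratum 2 Cycle A map (Section 4.4.2).
3. Mark the creatinine row of the Section 7.1 table in the pre-cycle induction column. This also brings the table into line with the Cycle B map, which needs no change.

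The cost is one routine blood value per Cycle A, on a day when blood is already drawn for counts, electrolytes and liver tests. That is at most three values in Stratum 1 (Cycles 1, 3 and 5) and four in Stratum 2. No statistical section needs amending.
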